1.0 Study Summary

Study Title	A cross sectional study of insulin resistance and cognitive function scores in patients with prostate cancer with or without androgen deprivation therapy (ADT)
Study Design	Cross sectional study
Primary Objective	To investigate the possible cellular and molecular mechanisms underlying insulin resistance in patients undergoing androgen deprivation therapy for prostatic carcinoma including determining the expression of insulin signaling genes and proinflammatory genes associated with insulin resistance.
Secondary Objective(s)	
1. Determine level of insulin resistance at different stages of ADT treatment compared to those not on ADT2. Correlate level of insulin resistance to the expression of insulin signaling genes and inflammatory mediators associated with insulin resistance3. Determine the effect of insulin resistance on body composition of men undergoing ADT4. Determine cognitive function scores in patients receiving ADT at various stages.
Research Intervention(s)/Investigational Agent(s)	None
IND/IDE #	NA
Study Population	Patients with Prostate cancer from Roswell Park Comprehensive Cancer Center
Sample Size	40
Study Duration for individual participants	Up to 7 days

University at Buffalo Institutional Review Board (UBIRB)

Office of Research Compliance | Clinical and Translational Research Center Room 5018
[name]
UB Federalwide Assurance ID#: FWA00008824

Study Specific Abbreviations/Definitions	
---	--

2.0 Objectives*

2.1 Describe the purpose, specific aims, or objectives of this research.

Response:

PRIMARY OBJECTIVE

To investigate the possible cellular and molecular mechanisms underlying or associated with insulin resistance in patients undergoing androgen deprivation therapy for prostatic carcinoma including determining the expression of insulin signaling genes and proinflammatory genes associated with insulin resistance.

SECONDARY OBJECTIVES

1. Determine level of insulin resistance at different stages of ADT treatment compared to those not on ADT
2. Correlate level of insulin resistance to the expression of insulin signaling genes and inflammatory mediators associated with insulin resistance
3. Determine the effect of insulin resistance on body composition of men undergoing ADT.
4. Determine cognitive function scores in patients receiving ADT at various stages.

2.2 State the hypotheses to be tested, if applicable.

NOTE: A hypothesis is a specific, testable prediction about what you expect to happen in your study that corresponds with your above listed objectives.

Response:

We hypothesize that ADT results in increase in insulin resistance and in inflammatory mediators which may interfere with insulin signal transduction. We hypothesize that ADT results in greater adiposity and an increase in plasma insulin and glucose concentrations with a concomitant increase in HOMA-IR, plasma TNF α and IL-1 β with a decrease in the expression of IR β , IRS-1, AKT and GLUT-4 in adipose tissue

3.0 Scientific Endpoints*

3.1 Describe the scientific endpoint(s), the main result or occurrence under study.

University at Buffalo Institutional Review Board (UBIRB)

Office of Research Compliance | Clinical and Translational Research Center Room 5018
[name]
UB Federalwide Assurance ID#: FWA00008824

*NOTE: Scientific endpoints are outcomes defined before the study begins to determine whether the objectives of the study have been met and to draw conclusions from the data. Include primary and secondary endpoints. Some example endpoints are: reduction of symptoms, improvement in quality of life, or survival. Your response should **not** be a date.*

Response:

PRIMARY ENDPOINTS

- Determine levels of IRS-1 serine phosphorylation in adipose tissue and MNC as marker of inflammation induced insulin resistance
- Changes in expression of insulin signaling genes; IR β , IRS-1 and AKT-2 in both adipose tissue and mononuclear cells and expression of GLUT-4 in adipose tissue in subjects with prostate cancer on ADT compared to those not on ADT
- Changes in expression of proinflammatory genes that interfere with insulin signaling transduction (TNF- α , IL-1 β , IKK- β , SOCS-3, PTB-1B, JNK-1, TLR-4) in adipose tissue and mononuclear cells will be assessed

SECONDARY ENDPOINTS

- Comparison in expression of insulin signaling genes and of proinflammatory genes associated with insulin resistance in adipose tissue and mononuclear cells among subjects with prostate cancer at various stages of ADT
- Measurement of insulin resistance by HOMA-IR method in subjects with prostate cancer on ADT compared to those not on ADT
- Correlation of insulin resistance as measured by HOMA-IR to the expression of insulin signaling genes and proinflammatory genes associated with insulin resistance in adipose tissue and mononuclear cells
- Changes in plasma levels of glucose, insulin and lipid concentrations in subjects with prostate cancer on ADT compared to those not on ADT
- Changes in plasma concentrations of inflammatory markers like free fatty acids (FFA), CRP (C-reactive protein), leptin, adiponectin, TNF- α and IL-1 β will be assessed
- Changes in lean body mass and fat mass; total and regional as measured by DEXA scan
- Changes in cognitive function scores in subjects with prostate cancer on ADT compared to those not on ADT

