ADT resulting in drastically low testosterone levels can have multitude of adverse effects on the metabolic, cardiovascular and bone health in men with prostate cancer. Prostate cancer patients receiving ADT experience bone loss, muscle loss and increased fat mass (sarcopenic obesity), and increased insulin resistance; thus leading to increased risk of development of Type 2 Diabetes Mellitus (T2DM). These changes can be seen as early as within 3 months of therapy and continue to occur even after 2 years on ADT therapy⁽⁵⁾. One of the earliest metabolic changes seen with ADT is hyperinsulinemia which is associated with fat mass increase. Sarcopenic obesity is a new term used for combination of excess weight and reduced muscle mass⁽⁶⁾. The earliest prospective study on body composition and insulin resistance following ADT in men with non-metastatic prostate cancer was conducted by Smith et al in 2001⁽⁷⁾. The study showed ADT in newly diagnosed men with PCa resulted in increase in fat mass from 20.2 ± 9.4 kg at baseline to 21.9 ± 9.6 kg at 3 months ($P=0.008$), while lean body mass decreased from 63.2 ± 6.8 kg at baseline to 61.5 ± 6.0 kg ($P=0.016$). Another prospective study confirmed these changes by showing that there was a 9.4% increase (p value < 0.001) in subcutaneous fat and 2.7% decrease (p value < 0.001) in lean mass after 12 months of ADT in 40 men⁽⁸⁾. Visceral fat did not change in this study. Similar findings were also observed in a recent study of 34 men receiving ADT and 29 men with prostate cancer but not receiving ADT⁽⁹⁾. Subcutaneous fat mass increased by 3.4 kg and lean mass decreased by 1.5 kg after 12 months of ADT.

University at Buffalo Institutional Review Board (UBIRB)

Office of Research Compliance | Clinical and Translational Research Center Room 5018
[name]
UB Federalwide Assurance ID#: FWA00008824

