5.0 Study Design*

- 5.1 Describe and explain the study design (e.g. case-control, cross-sectional, ethnographic, experimental, interventional, longitudinal, observational).

Response:

It will be a cross sectional study with 2 groups of patients.

University at Buffalo Institutional Review Board (UBIRB)

Office of Research Compliance | Clinical and Translational Research Center Room 5018
[name]
UB Federalwide Assurance ID#: FWA00008824

One group will be men with prostate cancer in various stages of ADT and the control group will be men with prostate cancer not on ADT.

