19.0 Data Management and Analysis*

19.1 Describe the data analysis plan, including any statistical procedures. This section applies to both quantitative and qualitative analysis.

Response:

The demographic features of the population and screening lab results will be displayed in tables. Statistical analysis will be carried out using SPSS and SigmaStat software (SPSS, IL). All data will be expressed as mean \pm S.E of arbitrary units and percent change is calculated from the means. To evaluate similarity between the study groups, baseline values for subject's demographics will be compared using appropriate parametric and non-parametric tests based upon the nature of the data

19.2 If applicable, provide a power analysis.

NOTE: This may not apply to certain types of studies, including chart/records reviews, survey studies, or observational studies. This question is asked to elicit whether the investigator has an adequate sample size to achieve the study objectives and justify a conclusion.

Response:

Based on our previous study, HH men have greater insulin resistance by 30% compared to eugonadal men. Therefore, a sample size of 20 patients in each group is sufficient to provide adequate power (80%) to detect a significant difference ($p<0.05$) in insulin resistance of $\geq 30\%$ between patients with ADT (negligible testosterone) and non-ATD patients (low to normal testosterone) assuming the standard deviation of the difference is $\leq 30\%$. and a drop-out rate of about 15%.

19.3 Describe any procedures that will be used for quality control of collected data.

University at Buffalo Institutional Review Board (UBIRB)

Office of Research Compliance | Clinical and Translational Research Center Room 5018
[name]
UB Federalwide Assurance ID#: FWA00008824

Response:

Three investigators and research nurse will double check the accuracy of collected data. All laboratory testing will be standardized using references and standards.

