21.0 Provisions to Monitor the Data to Ensure the Safety of Subjects*

- N/A:** This study is not enrolling subjects or is limited to records review procedures only. This section does not apply.

NOTE: Minimal risk studies may be required to monitor subject safety if the research procedures include procedures that present unique risks to subjects that require monitoring. Some examples include: exercising to exertion, or instruments that elicit suicidality or substance abuse behavior. In such cases, N/A is not an acceptable response.

21.1 Describe the plan to periodically evaluate the data collected regarding both harms and benefits to determine whether subjects remain safe.

Response:

We do not expect subjects to experience adverse reaction from fat biopsy procedures. However, patients will be under close monitoring by our staff during the entire process of the biopsy procedure. The investigators will assess other risks including the physical, psychological, social, legal and economic harm to these patients. The investigators listed above will carefully watch for any invasion of privacy and breach of confidentiality.

21.2 Describe what data are reviewed, including safety data, untoward events, and efficacy data.

Response:

University at Buffalo Institutional Review Board (UBIRB)

Office of Research Compliance | Clinical and Translational Research Center Room 5018
[name]
UB Federalwide Assurance ID#: FWA00008824

Blood Pressure, Height, Weight, and adverse reaction reported by subjects are monitored at the visit

21.3 Describe any safety endpoints.

Response:

NA

21.4 Describe how the safety information will be collected (e.g., with case report forms, at study visits, by telephone calls with participants).

Response:

On site during the visit. We also encourage participants to call us if they develop any adverse reaction

21.5 Describe the frequency of safety data collection.

Response:

The data collection will be done after all study visits

21.6 Describe who will review the safety data.

Response:

The safety data will be reviewed by the principle and sub investigators as well as the research coordinator

21.7 Describe the frequency or periodicity of review of cumulative safety data.

Response:

Safety data will be reviewed every three months during the duration of the study. Study endpoint data will be reviewed once after half of the recruited patients have completed the study and then at the end of the study

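### The DEXA lean-mass comparison is between different men scanned once, with no body-size adjustment planned; adding height as a covariate is a modest, nearly free gain, but the endpoint stays imprecise.

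*Combined protocol and SAP*

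**What the plan says.** Section 3.1 gives the endpoint as "Changes in lean body mass and fat mass; total and regional as measured by DEXA scan". It names no unit, index, covariate or comparator. Section 12.1 (Imaging) specifies appendicular and trunk regions and a single scan within 7 days of the fat biopsy.

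On design, section 5.1 says "It will be a cross sectional study with 2 groups of patients": men on ADT and controls with prostate cancer not on ADT. The hypothesis in section 2.2 is that ADT increases adiposity. Secondary objective 3 in section 2.1 is different: it concerns insulin resistance and body composition among men on ADT.

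The analysis plan in section 19.1 offers means with standard errors in unspecified units, percent change computed from the means, and tests of whether the groups' demographics are similar. It gives no model or adjustment for any endpoint. The only power calculation, in section 19.2, is for insulin resistance.

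The background figures in section 4.1 are mainly changes over time on ADT. In the 3-month study "lean body mass decreased from 63.2 ± 6.8 kg at baseline to 61.5 ± 6.0 kg", while fat mass rose from 20.2 ± 9.4 to 21.9 ± 9.6 kg. A later study, which also had men not on ADT, is cited for +3.4 kg of subcutaneous fat and -1.5 kg of lean mass at 12 months.

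Section 21.2 shows what else is recorded: "Blood Pressure, Height, Weight, and adverse reaction reported by subjects are monitored at the visit".

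**The concern.** In a study that measures the same men twice, each man is his own control and his build cancels out. Here it does not. A tall man has more lean mass than a short one whether or not he is on ADT, and that variation goes straight into the standard error of the group difference. The plan records height but does not use it.

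Two things are at stake. First, an interval several times wider than the changes cited in the background could easily be read as showing that ADT has no effect on body composition. Second, because neither scale nor adjustment is fixed, the choice between kilograms, percent fat and a height index could be made after the data are seen.

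**Working it through.** **Inputs from the documents.** 20 men per group and "a drop-out rate of about 15" percent (section 19.2), so 20 × 0.85 = 17 evaluable per group. Spreads of 6.8 kg lean and 9.4 kg fat (section 4.1, baseline values of the 3-month study). Changes of 1.7 kg lean and 1.7 kg fat at 3 months, and 1.5 kg lean and 3.4 kg subcutaneous fat at 12 months (section 4.1).

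**Assumptions.** The ± values are standard deviations, and tests are two-sided at 0.05. The documents give no correlation of lean mass with height (range 0.4 to 0.6 used) or of fat with lean mass (range 0 to 0.7), and no coefficient of variation of height (4% used).

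**The plan's own figure.** A 30% difference with a 30% SD is a standardised difference of 1. A two-sample t-test then has 78.1% power with 16 per group and 80.7% with 17, and 17/0.85 = 20. The stated 20 per group reproduces, for insulin resistance.

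**Precision of the unadjusted DEXA comparison.** Half-width = t(0.975, 32 df) × SD × √(2/17) = 2.037 × SD × 0.343.
- Lean: 2.037 × 6.8 × 0.343 = 4.75 kg.
- Fat: 2.037 × 9.4 × 0.343 = 6.57 kg.

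**Power of the unadjusted comparison** (noncentral t, 17 per group):

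| Quantity | Difference / SD | d | Power |
|---|---|---|---|
| Lean, 12 months | 1.5 / 6.8 | 0.22 | 9.6% |
| Lean, 3 months | 1.7 / 6.8 | 0.25 | 10.9% |
| Fat, 3 months | 1.7 / 9.4 | 0.18 | 8.0% |
| Fat, 12 months (subcutaneous change against total-fat SD) | 3.4 / 9.4 | 0.36 | 17.6% |

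The last row mixes two quantities and is only an indication.

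**Lean mass with height as a covariate.** Residual SD = 6.8 × √(1 − r²); equivalent gain in sample size = 1/(1 − r²); 31 df.

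| r | Residual SD | Gain | Half-width | Power, 1.5 to 1.7 kg |
|---|---|---|---|---|
| 0.4 | 6.23 kg | 1.19 | 4.36 kg | 10.4 to 12.0% |
| 0.6 | 5.44 kg | 1.56 | 3.81 kg | 12.2 to 14.3% |

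**Lean mass divided by height squared.** Simulated with the pooled SD √((6.8² + 6.0²)/2) = 6.41 kg, the index has a spread equivalent to 8.16 kg at r = 0, 6.39 kg at r = 0.4 and 5.29 kg at r = 0.6. It gains almost nothing at 0.4 and loses precision below that. The covariate approach cannot lose more than the one degree of freedom and the small cost of any chance height imbalance.

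**Percent fat.** From the 3-month means, 20.2/(20.2 + 63.2) = 24.2% and 21.9/(21.9 + 61.5) = 26.3%, a shift of about 2.0 points. With log-normal fat mass and the correlation range above, the simulated SD is 8.0 to 6.6 points, d is 0.25 to 0.31, and power with 17 per group is 11 to 14%, against 8.0% for fat mass. The advantage is already present at a fat-lean correlation of 0, where there is no shared size component to remove. It therefore comes partly from adding the lean loss to the fat gain.

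**The case against.** The strongest reply is that this improvement is too small to matter. Moving lean-mass power from 10-11% to 10-14% does not rescue the endpoint; the limit is the number of men, and this is one of seven secondary endpoints. That stands, and it is why the point is confined to a modest gain and to how the result is reported. It does not argue for leaving a recorded covariate unused.

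A reader might go further than the documents allow in four ways:
- That the plan commits to a raw-kilogram comparison. It does not; it states no scale. The supportable criticism is that no scale or adjustment is specified.
- That body size is the main source of the spread. Section 4.1 gives total spreads, not their causes. A height correlation of 0.4 to 0.6 explains only 16 to 36% of lean-mass variance, and much of the fat-mass spread may be adiposity itself, which height cannot remove.
- That percent fat is simply a sharper version of fat mass. It answers a different question, because fat gain and lean loss can no longer be told apart.
- That chance height imbalance is a further error on top of the interval. It is already inside the half-width of 4.75 kg.

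The DEXA entry in section 3.1 also names no comparator, so the group comparison is inferred from sections 2.2 and 5.1. Finally, the true differences could exceed the cited ones: entry requires at least 3 months of ADT, and section 4.1 describes changes continuing past 2 years. That would raise power, but it does not weaken the case for adjusting for height.

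**Conclusion.** The point holds as a low-cost improvement, not as a flaw that invalidates the endpoint. As planned, the DEXA comparison would carry a half-width of about 4.8 kg for lean and 6.6 kg for fat, roughly three and four times the 3-month changes of 1.7 kg (4.75/1.7 = 2.8; 6.57/1.7 = 3.9). Height adjustment narrows the lean half-width to somewhere between 4.4 and 3.8 kg, equivalent to 1.2 to 1.6 times the sample size, if the correlation lies between 0.4 and 0.6.

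Neither height adjustment nor percent fat makes the endpoint adequately powered for the 3-month changes. The figures rest on reading ± as standard deviations, on 17 evaluable men per group, and on correlations that the documents do not give. The entry limit of BMI above 25 may make the spreads in this study differ from those in section 4.1.

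**What to change.** In sections 3.1 and 19.1:
- State the DEXA comparison as the ADT-minus-control difference with a 95% confidence interval.
- Analyse total and appendicular lean mass by ANCOVA with height as the covariate. Do not divide by height squared, and do not adjust for weight or BMI, since ADT may alter both.
- Report percent fat (total and trunk) alongside fat mass, not in place of it. It speaks to the adiposity hypothesis but combines fat gain with lean loss.
- Label the endpoint exploratory, and say in advance that an interval including zero will be described as imprecise, not as evidence of no effect.

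The cost is a change of wording and one degree of freedom. No new measurement is needed: height is recorded at the visit, and fat and lean mass come from the same scan.

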4.0 Background*

University at Buffalo Institutional Review Board (UBIRB)

Office of Research Compliance | Clinical and Translational Research Center Room 5018
[name]
UB Federalwide Assurance ID#: FWA00008824

4.1 Provide the scientific or scholarly background, rationale, and significance of the research based on the existing literature and how it will contribute to existing knowledge. Describe any gaps in current knowledge. Include relevant preliminary findings or prior research by the investigator.

Response:

Prostate cancer (PrCa) is the most common non-cutaneous malignancy amongst men in the United States. Early stage, organ-confined PrCa can be cured by surgery or radiotherapy. While the majority of men are diagnosed with early stage disease, many present with more advanced disease or are otherwise not good candidates for curative therapies. In addition, one third of patients with localized disease will eventually develop metastatic PrCa. The mainstay treatment of locally advanced, as well as recurrent or metastatic PrCa is androgen deprivation therapy (ADT)^[1], which blocks the production of male hormones and induces tumor cell apoptosis^[2].

ADT either via castration or more frequently, gonadotropin-releasing hormone (GnRH) agonists (such as leuprolide), reduces serum testosterone (T) to castrate levels^[3]. Despite initial responses, almost all patients will eventually develop disease progression, which in the presence of continuous ADT is defined as castration resistant PrCa (CRPC). Some CRPC patients may respond for a number of years to sequential administration of more potent anti-androgens combined with ongoing continuous ADT^[4]. Thus, it is not unusual for men with advanced PrCa to be on continuous ADT for many years.

ADT resulting in drastically low testosterone levels can have multitude of adverse effects on the metabolic, cardiovascular and bone health in men with prostate cancer. Prostate cancer patients receiving ADT experience bone loss, muscle loss and increased fat mass (sarcopenic obesity), and increased insulin resistance; thus leading to increased risk of development of Type 2 Diabetes Mellitus (T2DM). These changes can be seen as early as within 3 months of therapy and continue to occur even after 2 years on ADT therapy⁽⁵⁾. One of the earliest metabolic changes seen with ADT is hyperinsulinemia which is associated with fat mass increase. Sarcopenic obesity is a new term used for combination of excess weight and reduced muscle mass⁽⁶⁾. The earliest prospective study on body composition and insulin resistance following ADT in men with non-metastatic prostate cancer was conducted by Smith et al in 2001⁽⁷⁾. The study showed ADT in newly diagnosed men with PCa resulted in increase in fat mass from 20.2 ± 9.4 kg at baseline to 21.9 ± 9.6 kg at 3 months ($P=0.008$), while lean body mass decreased from 63.2 ± 6.8 kg at baseline to 61.5 ± 6.0 kg ($P=0.016$). Another prospective study confirmed these changes by showing that there was a 9.4% increase (p value < 0.001) in subcutaneous fat and 2.7% decrease (p value < 0.001) in lean mass after 12 months of ADT in 40 men⁽⁸⁾. Visceral fat did not change in this study. Similar findings were also observed in a recent study of 34 men receiving ADT and 29 men with prostate cancer but not receiving ADT⁽⁹⁾. Subcutaneous fat mass increased by 3.4 kg and lean mass decreased by 1.5 kg after 12 months of ADT.

University at Buffalo Institutional Review Board (UBIRB)

Office of Research Compliance | Clinical and Translational Research Center Room 5018
[name]
UB Federalwide Assurance ID#: FWA00008824

Several retrospective and prospective studies have shown increased risk development of insulin resistance and T2DM in PCa patients receiving ADT. In the same study done by Smith et al⁽⁷⁾, they also showed increase in serum fasting serum insulin levels from 11.8 mU/L at baseline to 19.3 mU/L at 3 months. A short term study showed statistically significant increase in fasting serum glucose levels in PCa patients on ADT for 6 months suggesting compensatory hyperinsulinemia⁽¹⁰⁾. A cross sectional study by Basaria et al, which recruited men on ADT for at least 12 months and age matched men with PCa not on ADT, showed hyperinsulinemia and fasting hyperglycemia more prevalent in ADT group than the control group^(11,12) and the severity of these metabolic complications was directly related to the duration of ADT⁽¹²⁾. Subsequent population based study looked into the health data of 73,196 men > 66 years old and showed that men undergoing ADT experienced a 44% increase in development of diabetes than men not undergoing ADT⁽¹³⁾. Similar analysis of a Canadian Database with an age matched cohort study including about 20,000 men > 66 years of age treated for prostate cancer found increased risk of diabetes (by 16%) in men treated with ADT compared to ADT naïve men⁽¹⁴⁾. These men were followed for an average of 6.47 years. Thus, long term ADT has been shown to cause increased incidence of sarcopenic obesity, insulin resistance and T2DM, all leading to increased adverse metabolic and cardiovascular outcomes.

Studies have shown an increase in insulin resistance as measured by HOMA of insulin resistance (HOMA-IR) in subjects with low Testosterone levels irrespective of diabetes^(15,16). And this is mediated through an increase in inflammatory mediators that interfere with insulin signaling. Our previous study on hypogonadal men in T2DM have shown that patients with hypogonadotropic hypogonadism (HH) have an increase in insulin resistance and increase in inflammatory mediators, which may interfere with insulin signal transduction⁽¹⁷⁾. Our results clearly showed that type 2 diabetes patients with HH had significant increase in insulin resistance (as measured by hyperinsulinemic-euglycemic clamps, decreased GIR by 36%) compared to the type 2 diabetes patients without HH. There was a marked reduction in expression of IR-β, IRS-1, AKT-2 and GLUT-4 in adipose tissue, the major genes mediating insulin signaling in the adipose tissue in HH men compared to eugonadal men. We also showed in the same study, that replacement of testosterone for 6 months lead to an increase in insulin sensitivity (measured through HE clamps), significant increase in the expression of above genes in adipose tissue and suppression of inflammatory mediators which interfere with insulin signaling. This explains the mechanism of increased insulin resistance in hypogonadal men reversed by testosterone supplementation.

Several reports have also linked the use of ADT to cognitive decline in men with prostate cancer^[18]. Gonzales et al. reported in patients on ADT for prostate cancer had a statistically significant impairment in cognitive function compared to an education and age matched cohort of patient not on ADT as early as 6 months^[19]. A recently published large retrospective analysis of more than 150,000 patients with prostate cancer who were followed for a period of at-least 10 years showed an increase in the diagnosis of Alzheimer's disease (AD) and dementia in patients treated with ADT compared to patient

University at Buffalo Institutional Review Board (UBIRB)

Office of Research Compliance | Clinical and Translational Research Center Room 5018
[name]
UB Federalwide Assurance ID#: FWA00008824

who did not receive ADT. The HR for AD and dementia was proportional to the doses of ADT with higher HR seen in patients who received >4 doses of ADT^[20].

4.2 Include complete citations or references.

Response:

